3.3.1. Reactive case detection (RACD)

Household RACD

Within 7 days of the index case notification, the VMW will conduct the investigation visit at the residence of the index, and the index case will be interviewed using a standard case investigation form. All members of the index case's household will then be invited to participate in the study. A GPS point will be captured for the index house, and the nearest five households around the index case's household will be identified by the VMW. In the neighboring five households, a GPS point will be captured and all household members, including temporary visitors, will be invited to participate in the study. Household members and parents/guardians of children will be verbally informed of the general purpose of the intervention and the study, and the possible risks and potential benefits associated with participation. Individual written consent will be obtained at each household and for each blood sample collected for testing. For children <6 to 12 years old, consent will be obtained from the parent or guardian. For children 12 to <18 years of age, the child's oral assent will also be required in addition to parents/guardians' consent. All informed consent procedures will be conducted in the appropriate local language. All consenting participants will be interviewed using the participants' questionnaire to assess history of malaria in previous year, travel information, and utilization of malaria prevention measures.

A finger stick blood sample will be collected for each consenting individual for testing with the HS-RDT for *P. falciparum*, a standard combination RDT, and four blood spots on filter paper. Individuals will be told of their test result and a positive test result on either RDT will prompt treatment as per the national treatment guidelines. See tables 2 and 3 below for treatment guidelines.

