All individuals who test positive by either HS-RDT or Standard RDT will be told of their results and treated on site per national guidelines:

- Individuals with *P. falciparum* infection will be treated with an age-appropriate course of artemether-lumefantrine (AL) and a single low dose of primaquine (SLD-PQ). Weight-based dosing is described in Tables 2 and 3 below.
- At all study sites in Lao PDR, patients with a *P. vivax* infection identified by RDT (both febrile and asymptomatic) will be given a unique coded and signed informational letter directing them to the nearest district hospital (or other testing facility) for G6PD deficiency testing and possible radical cure administration depending on results. Study contact information will also be included if the participants present at other health facilities. At the health facility, G6PD normal individuals will be treated with AL and a 14-day course of PQ, whereas G6PD deficient individuals will receive AL alone as per the national guidelines and referred to a hospital for further primaquine management decisions. The study staff will meet with district hospital and health facility staff monthly from all study areas and nearby district hospitals and health facilities to collect these forms, with small incentives for health staff to report receiving a study card (phone top up card, etc.) to maximize data completeness. After six months of implementation, a subset of VMWs will begin conducting qualitative G6PD testing and treatment administration at the community-level with the assistance of a health facility staff member.

Table 2. AL weight-based dosing

Body weight (kg)	Tablet strength (mg)		Tablets/dose	Mg of drug per dose		Tablets/day
	Artemether	Lumefantrine		Artemether	Lumefantrine	
5 to 14	20	120	1	20	120	1 tablet given twice* per day for 3 consecutive days

15 to 24	20	120	2	40	240	2 tablets given twice* per day for 3 consecutive days
25 to 34	20	120	3	60	360	3 tablets given twice* per day for 3 consecutive days
35 or greater	20	120	4	80	480	4 tablets given twice* per day for 3 consecutive days
*Approx. 8 hours between doses 1 and 2. Approx. 12 hours between all other consecutive doses.						

Table 3. Weight-based dosing of SLD- Primaquine (.25 mg/kg) for *P. falciparum*

Body weight (kg)	SLD-PQ dose (7.5 mg tablet) (as base)	Tablets
10 to < 25	3.75	1/2
25 to < 50	7.5	1
50 to 100	15	2
*Given as SLD in addition to AL for P falciparum positive		

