Table 4. Age-based dosing of Primaquine for *P. vivax*

Items	Dose	No. of tablet/day	Frequency	Duration
G6PD Normal				
Children				
4-8 years old	5 mg/day	1/3	Once per day after meal	14 days
9-14 years old	10 mg/ day	2/3		
>14 years old (adults)	15 mg/ day	1		

Per national guidelines in Laos, AL will not be given to women who are pregnant or may be in their first trimester. All women of reproductive age with a last menstrual period greater than four weeks positive HS RDT or Standard RDT will be offered a pregnancy test. Pregnancy testing and consent will be embedded in the participant questionnaire. Any woman who acknowledges pregnancy in the first trimester or confirmed by a positive pregnancy test or refuses to take a pregnancy test will be excluded from receiving AL and will be referred to the nearest health facilities for treatment.

Contraindications to primaquine include pregnancy (any trimester), age less than 12 months, infants weighing less than 10 kilograms, women in the first 12 months of breastfeeding, and prior allergic reaction to primaquine. Participants with contraindications to primaquine will not be excluded from the study and will receive first-line treatment alone, provided they are eligible.

All individuals with suspected severe malaria or other severe illness (including those with symptoms of severe anemia, prostration, impaired consciousness, respiratory distress, convulsions, circulatory collapse, abnormal bleeding, jaundice or passing dark urine) will be referred to the nearest health facility for clinical assessment and treatment.

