3.4.2.2. Randomization

A total of 32 health center catchment areas (HCCAs) in Laos will be selected for inclusion based upon incidence per 1000 population between October 2017 and September 2018. HCCAs with higher incidence will be prioritized to improve power; where possible, directly neighboring HCCAs will not both be included to reduce contamination. Restricted randomization of the HCCAs into either RACD or control arms will be conducted, whereby sets of randomizations (with 16 HCCAs in each arm) will be generated that achieve balance across arms on incidence per 1,000 over the prior year, population size, and amount of forest cover. From these sets of potential randomizations, a single randomization will be randomly selected to assign 16 HCCAs each to the RACD or control group. Restricted randomization in this way will ensure balance across intervention and control groups on potential confounding factors. The 'sample' command in Stata v14 (StataCorp, College Station, TX) will be used to implement randomization.

Table 5. Study arms

Study arm	Description	Lao PDR
RACD	Reactive case detection led by VMWs in response to cases in study area HCCA, with follow up testing with HS-RDTs/RDTs in both villages and forest workers; referrals for qualitative G6PD testing for P. vivax cases and 14-day PQ for G6PD non-deficient	16
Control	Standard of care including case management through health facilities and malaria posts/VMWs; village-based RACD conducted by district staff in some areas	16

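### The P. vivax treatment text contradicts itself: all RDT positives are to be treated on site, yet artemether-lumefantrine is placed at the referral facility, and nothing is stated for those who do not attend

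*Protocol*

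**What the plan says.** Section 3.3.1, under Case Management and Follow-up, begins with a general rule: "All individuals who test positive by either HS-RDT or Standard RDT will be told of their results and treated on site per national guidelines". Two bullets follow. The P. falciparum bullet names AL with a single low dose of primaquine, which fits the rule.

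The P. vivax bullet covers people with and without fever at all study sites. It gives them a letter "directing them to the nearest district hospital (or other testing facility) for G6PD deficiency testing and possible radical cure administration depending on results". For people who prove G6PD normal it then says: "At the health facility, G6PD normal individuals will be treated with AL and a 14-day course of PQ". The remainder of that sentence deals with the other group: "whereas G6PD deficient individuals will receive AL alone as per the national guidelines and referred to a hospital for further primaquine management decisions". The bullet names no drug to be given where the person tested positive. The one stated departure from this route comes after six months, when "a subset of VMWs will begin conducting qualitative G6PD testing and treatment administration at the community-level".

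**The concern.** The general rule and the P. vivax bullet give different answers to a simple question: does a person found P. vivax positive at a reactive case detection (RACD) visit receive AL then and there? The rule says yes. The bullet, read literally, says only after reaching a facility. Both G6PD groups are to receive AL, so nothing in the treatment choice requires AL to wait for the G6PD result; only the 14-day primaquine course depends on it.

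This is a matter of participant safety. Section 2.6 tells readers that people found infected by RDT benefit directly from first-line treatment. A person given only a letter, who then does not travel, has a diagnosed infection and no blood-stage treatment from the study. Routine care remains open (Section 4.4), but the bullet expressly includes people without symptoms, who have no illness to prompt them to seek it.

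**Working it through.** No figure in the plan is in dispute, so the check is a comparison of texts, followed by one ratio for duration and one for context.

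**Step 1. Does another section say that the VMW gives AL to a P. vivax positive at the visit?**

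- Section 3.3, Index case capture: confirmed index cases are treated according to national guidelines. Neither species nor place of AL is specified.
- Section 3.3.1, Household RACD: "a positive test result on either RDT will prompt treatment as per the national treatment guidelines". The reader is sent to Tables 2 and 3, which give AL dosing and the single low primaquine dose for P. falciparum. Positives found at a revisit are also to be treated. AL for P. vivax on site is not stated.
- Section 3.3.1, peer-referral and venue-based RACD: treatment follows the guidelines in the next section, which is the text in question.
- Section 3.3.1, after Table 4: a woman in the first trimester, with a positive pregnancy test or refusing one "will be excluded from receiving AL and will be referred to the nearest health facilities for treatment". This makes facility treatment look like an exception, but does not mention P. vivax. People with primaquine contraindications get first-line treatment alone; this does not address non-attendance.
- Section 3.4.2.2, Table 5: the intervention arm has referrals for qualitative G6PD testing of P. vivax "cases and 14-day PQ for G6PD non-deficient". AL is not mentioned.
- Section 3.4.2.5.3: the letter is for G6PD testing and the treatment that follows. Whether that treatment includes AL is not stated.
- Section 4.2: referral is tied to G6PD testing and the 14-day course.
- Section 4.3: a curative benefit of AL is claimed for the RACD arm, without species or place.

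Several of these are compatible with AL on site. None states it for P. vivax, and the only text that says where a P. vivax positive receives AL says the facility.

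**Step 2. Is there a provision for people who do not attend?**

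- The Section 3.3.2 follow-up visits on days 3, 7 and 14 are for people already treated with primaquine for P. vivax, so they do not reach non-attenders.
- The monthly facility meetings in Section 3.3.1 collect the referral forms and serve data completeness. Tracing non-attenders is not mentioned.
- Section 3.4.1 (Activity 3) and Section 3.4.3.2 measure attendance for G6PD testing; Activity 3 also sets out to find risk factors for non-attendance. Section 3.4.3.5, Outcome 5, compares people tested with people not tested. Non-attendance is therefore expected, but no treatment is stated for it.

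**Step 3. Duration.** Inputs: six months before the VMW subset starts (Section 3.3.1); 18-month study period (Section 1).

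Share of the period in which referral is the only stated route = 6 / 18 = 0.33.

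Afterwards referral still applies wherever a VMW is outside the subset, whose size is not given.

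**Step 4. Context.** In Table 1 (Section 3.1), the baseline annual parasite index is 2.79 for P. vivax out of 6.77 in total: 2.79 / 6.77 = 0.41. This is the P. vivax share of reported baseline cases, not its share among RACD contacts.

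**Step 5. Number affected.** This would need the P. vivax yield among people tested, the referral attendance rate and the size of the VMW subset. The protocol gives none of them, so no count is attempted.

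**The case against.** The strongest reply is that AL on site was intended all along and only the G6PD test and 14-day primaquine were meant to be referred. The bullet sits under a sentence that already says everyone is treated on site. The letter's stated purpose is G6PD testing and possible radical cure, and AL does not depend on the G6PD result. The facility sentence can then be read as the full regimen for each G6PD group. The attendance outcomes concern G6PD testing, so they do not show that anyone is expected to go without AL. The national guidelines, the SOPs mentioned in Section 3.4.3.5 and the VMW referral form (Appendix 8.11) may settle the matter in the field.

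Much of this stands. The benign reading is possible and may well be the intent. The harm is conditional on a VMW following the bullet, and the 33% describes how long referral is the only stated route, not how many people go untreated. The gap is also most plausible for RACD contacts, because confirmed index cases fall under routine treatment in Section 3.3. A person also positive for P. falciparum would receive AL under the first bullet.

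None of this removes the contradiction. The benign reading requires the VMW to set aside the only text that says where a P. vivax positive receives AL. Two readings with opposite consequences for a diagnosed infection should not both be open in the protocol.

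**Conclusion.** The concern holds and should be fixed. That the wording is inconsistent, and that no treatment is stated for a referred person who does not attend, can be said with high confidence. How many people, if any, would go without AL cannot be said. The finding rests on the protocol text alone; the national treatment guideline was not available and could show which reading is correct. No effect on a trial outcome is claimed.

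**What to change.** Amend the P. vivax bullet in Section 3.3.1 to state that the VMW gives AL at the RACD visit to every P. vivax positive without an AL contraindication (as listed in Sections 3.3.1 and 3.3.2), and that the letter refers the person only for G6PD testing and, if G6PD normal, 14-day primaquine. This agrees with the opening sentence and should be confirmed against the national guideline.

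If the guideline does not allow it, limit the on-site rule to P. falciparum and state how referred people who do not attend are traced and offered AL.

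The first option costs protocol and SOP wording plus brief VMW retraining; VMWs already give AL on site for P. falciparum. The second also needs a tracing step for non-attenders.

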Safe and effective management of *P. vivax* cases requires addressing glucose-6-phosphate dehydrogenase (G6PD) deficiency and ensuring patients with G6PD normal function complete a 14-day treatment regimen with primaquine. The heterogeneity and severity of G6PD deficiencies in SE Asia and associated risk of severe hemolysis with oxidative drugs such as primaquine is an especially serious public health issue⁸. The majority of *P. vivax* cases in most transmission settings are due to relapses⁹, making primaquine (and tafenoquine when available) a critical component of elimination activities. However, treatment adherence for full 14-day primaquine is generally sub-optimal, and standard of care use of primaquine in health systems has shown minimal effectiveness in preventing relapses¹⁰. There are limited data on primaquine use in Lao PDR; a study conducted by WHO and CMPE in 2015 enrolled 1,577 *P. vivax* cases (363 women) for G6PD testing of which 67 (4.2%; 95% CI: 3.3 to 5.3%) were classified as deficient.¹¹ A total of 1,225 G6PD non-deficient individuals with *P. vivax* infection were enrolled for PQ administration, of which 889 (72.5%) completed follow-up hematocrit testing, and only one individual experienced a serious drop in hematocrit (below 25%). However, treatment adherence and parasite clearance were not measured in the study. This study and others

suggest that there remain key gaps in knowledge to inform safe and effective programmatic use of primaquine drug regimens to target the hypnozoite reservoir, especially with regards to ensuring adequate follow-up and safety monitoring at all levels of the health system including the community level.

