3.3.2. Adherence and safety monitoring

To ensure participants' adherence to their medication and monitor safety, participants will be informed on how to take their medications, about the side effects of the treatment and the importance of compliance to the treatment. In addition to DOT on day 0, The VMW will conduct a day

3, day 7, and day 14 adherence and safety monitoring visit for all individuals treated with primaquine for *P. vivax*, and the VMW will ask a series of questions to determine adherence with each dose, number of remaining tablets, potential adverse events, and reasons for non-adherence or treatment refusal. Participants with phone number will be sent a daily text message to remind them to adhere to their treatment and remind them about any symptoms suggesting serious adverse events. All participants and their family members will be provided a chart to record and track their adherence as well as symptoms that may indicate an adverse event.

The safety risks associated with participation in this trial are expected to be minimal. The study drugs, AL and PQ, are well tolerated first-line treatments and safe for G6PD non-deficient individuals. Prior to drug administration, participants will be asked about known contraindications, and if such contraindications are reported, participants will be restricted from taking the medication.

Drug	Contraindications
AL	Pregnancy, infants < 5kg, prior allergic reaction, any severe disease
PQ	Pregnancy, age < 12months, infants < 10kg, women in first 12 months of breastfeeding, prior allergic reaction, any severe disease, G6PD deficient

The common adverse events reported for each drug are as below:

- AL: headache, dizziness, loss of appetite, generalized weakness, fever, chills, arthralgia, myalgia, nausea, vomiting, and abdominal pain
- PQ: nausea, headache, fatigue, dizziness, hives, chest pain, painless darkening of urine, jaundice of skin and vomiting.

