4.2. Protection against risks associated with administration of PQ

The main safety concern for primaquine administration is the risk of acute hemolytic anemia in individuals with glucose-6-phosphate dehydrogenase (G6PD) deficiency¹⁷. In a context where G6PD testing is not available, a dose of 0.25mg/kg of PQ has been found to be safe in individuals with any of the G6PD variants and is recommended by WHO¹³. All individuals RDT+ for *P. vivax* will be referred to and tested at a health facility using a G6PD Carestart RDT and a 14-day course of primaquine will only be given to G6PD non-deficient individuals. After the first six months, a subset of VMWs will conduct G6PD testing under supervision by a study staff member for *P. vivax* cases diagnosed in the community. Primaquine is typically well tolerated but possible side effects include nausea, headache, fatigue, dizziness, hives, chest pain, painless darkening of urine, jaundice of skin, vomiting and syncope (fainting). In line with national guidelines, PQ will not be administered to pregnant women in any trimester or to women unable to undergo pregnancy testing, children less than 6 months of age, infants weighing less than 10 kg, women in the first 6 months of breastfeeding, or individuals with prior allergic reaction to PQ or related drugs.

The key to managing side effects and any potential adverse events (AEs) or serious AEs (SAEs) is thorough training of VMWs/VHVs, health facility staff and supervisors, and intensive sensitization of the community. HC workers and VMWs/VHVs will passively monitor their respective communities for AEs and refer any potential SAEs to designated health facilities. Health workers at these facilities will be informed of the project and potential side effects, and undergo training on completion of AE reporting forms (8.14 and 8.15). Cases that cannot be treated at health centers will be referred to district or provincial hospitals.

All participants receiving study drug will be provided with an informational sheet listing potential side effects and instruction to seek care at the nearest health center should they experience any of the defined symptoms or other adverse events. Community sensitization events and targeted IEC/BCC materials will also help increase community awareness of potential adverse events and encourage early care-seeking if events arise.

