4.6.2. Inclusion of vulnerable subjects – children and pregnant women

All age groups will be included in this study, except for those < 18 months. All children that participate must have the consent of the parent or guardian. Children older than 6 years and less than 18 must also provide oral assent before participation. All women who are pregnant or believe they may be pregnant will be assessed appropriately before treatment.

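### Primaquine is barred up to 12 months of breastfeeding in Protocol sections 3.3.1 and 3.3.2 but only up to 6 months in section 4.2, and nothing says which limit applies

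*Protocol*

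**What the plan says.** Three places in the protocol list who may not receive primaquine.

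- Section 3.3.1 (Case Management and Follow-up) includes "age less than 12 months, infants weighing less than 10 kilograms, women in the first 12 months of breastfeeding". Those concerned stay in the study: "Participants with contraindications to primaquine will not be excluded from the study and will receive first-line treatment alone".
- The contraindication table in section 3.3.2 includes "women in first 12 months of breastfeeding, prior allergic reaction, any severe disease". The text above that table makes the list a check before dosing: "participants will be asked about known contraindications, and if such contraindications are reported, participants will be restricted from taking the medication".
- Section 4.2 (risks of primaquine) says, with reference to national guidelines, that the drug will not be given to "children less than 6 months of age, infants weighing less than 10 kg, women in the first 6 months of breastfeeding".

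For anyone not excluded, section 3.3.1 makes primaquine part of standard treatment. Falciparum infections receive a single low dose with artemether-lumefantrine. For vivax, "G6PD normal individuals will be treated with AL and a 14-day course of PQ".

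**The concern.** A contraindication list has to give one answer for each patient. For a woman who has been breastfeeding for between 6 and 12 months, this protocol gives two. Staff working from section 3.3.1 or 3.3.2 would withhold primaquine. Staff working from section 4.2 would find no reason to withhold it, and standard treatment includes it.

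Either error has a cost. If 12 months is the right limit, section 4.2, where the protocol sets out its protection against primaquine risk, describes weaker protection than the treatment section gives. The G6PD test in section 3.3.1 is done on the patient, and these sections provide no test for the nursing infant. If 6 months is right, sections 3.3.1 and 3.3.2 withhold radical cure from vivax patients who could have it. Much of the treatment is given on site, and after six months a subset of village malaria workers begins G6PD testing and treatment in the community with help from a facility staff member, so the screening question needs one clear cut-off.

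**Working it through.** **Text comparison.** No planned figure is involved in the contradiction itself, so the check is to set the lists side by side.

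| Place | Breastfeeding limit | Age limit | Weight limit | Regimen named? |
|---|---|---|---|---|
| 3.3.1 | 12 months | 12 months | 10 kg | no |
| 3.3.2 table | 12 months | 12 months | 10 kg | no |
| 4.2 | 6 months | 6 months | 10 kg | no |

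Could the limits belong to different regimens? Sections 3.3.1 and 3.3.2 speak of primaquine in general. Section 4.2 discusses both the 0.25 mg/kg dose and the 14-day course and then gives one exclusion list. No list is limited to an arm or a period of the study, and no sentence says which prevails. The 6-to-12-month band is therefore in conflict for both regimens.

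The age limits conflict in the same way, with little effect in practice. Section 4.6.2 says "All age groups will be included in this study, except for those < 18 months", and all three lists share the 10 kg limit.

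**Rough number of women.** Inputs from the protocol:

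- 17,280 people tested in reactive case detection, from 720 cases (section 3.4.2.4.3).
- 400 people in each of 32 catchments tested at endline, with 2.5% control prevalence by qPCR and a 50% reduction (section 3.4.2.4.2).
- Vivax share 2.79/6.77 of cases (Table 1).
- 363 women among 1,577 vivax cases in an earlier Lao study (section 2).

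Assumptions, not in the protocol: one birth-year cohort is 2–3% of the population; women are half the population; all mothers still breastfeed at 6–12 months; the sex ratio of that vivax study holds for every group below.

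- Women 6–12 months after a birth: half of 2–3% = 1–1.5% of the population.
- Relative risk in women: (363/1,577)/0.5 = 0.230/0.5 = 0.46.
- Reactive case detection: 17,280 × 0.2% = 35 positives to 17,280 × 2.5% = 432 positives. Women in the band: 35 × 1% × 0.46 = 0.2 to 432 × 1.5% × 0.46 = 3.0.
- Endline, upper: 6,400 × 2.5% + 6,400 × 1.25% = 240 positives; 240 × 1.5% × 0.46 = 1.7. Lower, at 0.2%: 12,800 × 0.2% = 26; 26 × 1% × 0.46 = 0.1.
- Vivax index cases in the referral route: 720 × 2.79/6.77 = 297; 297 × 1–1.5% × 0.46 = 1.4 to 2.0.
- Total: 0.2 + 0.1 + 1.4 = 1.7 to 3.0 + 1.7 + 2.0 = 6.7. If 70% still breastfeed: 1.2 to 4.7.

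The 0.2% (a PCR yield from Thailand, section 2) and the 2.5% are molecular figures, whereas treatment follows a positive RDT or HS-RDT. Within one population a rapid test would be expected to find fewer infections than PCR, but contacts of cases may have higher prevalence than the general population. Some vivax patients will also not complete referral or G6PD testing. The range shows order of magnitude only. Counting the endline group also assumes that its treatment pointer, to a section 3.1.1 that does not exist, means section 3.3.1.

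**The case against.** The best case for leaving the text alone is that sections 3.3.1 and 3.3.2 are the operational text, agree with each other, and can be followed without breaching section 4.2, because withholding the drug satisfies all three lists. Section 4.2 sits in the ethics chapter, and the likely result in the field is withholding, not unsafe dosing. That is a fair account of how the conflict might play out. It does not remove the conflict, since no clause makes the stricter list prevail and one stated limit must be wrong.

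Three stronger readings are tempting, and the document does not support them.

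- A reader might infer that section 4.2 orders primaquine for women at 6 to 12 months. It only lists who will not receive it. The drug becomes due through the standard treatment in section 3.3.1.
- A reader might infer that section 4.2 is the error because it is outnumbered two to one. It is, however, the only list that expressly ties its primaquine limits to national guidelines. In section 3.3.1 the general appeal to those guidelines covers treatment as a whole, and the nearer one concerns artemether-lumefantrine in pregnancy. The document does not show which limit the guideline contains.
- A reader might count affected women across all 720 index cases, which gives 720 × 1–1.5% × 0.46 = 3.3 to 5.0. Section 3.3 (Index case capture) has index cases treated under national guidelines at diagnosis, around enrolment, so these lists do not clearly govern them. The exception is vivax patients whom the study refers for G6PD testing (section 3.4.2.5.3).

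**Conclusion.** The contradiction is certain. The protocol sets two different breastfeeding limits for the same drug, with no regimen distinction and no rule of precedence, and women breastfeeding at 6 to 12 months fall between them. Its reach is small: a handful of women, about 2 to 7 on assumptions about birth rate, breastfeeding duration, sex ratio and test positivity that the protocol does not supply. It is a drug-safety wording error with no effect on sample size or on any analysis. Which limit is correct cannot be decided from the protocol. The mismatch in minimum age is part of the same inconsistency but has almost no practical consequence, given the 18-month entry age. The appended forms are not shown. They may use a single limit, but that would not correct the protocol text.

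**What to change.** Confirm the limit in the national guideline and state that one limit in sections 3.3.1, 3.3.2 and 4.2, aligning the minimum age (12 or 6 months) in the same amendment. If the guideline says 12 months, section 4.2 changes. If it says 6, sections 3.3.1 and 3.3.2 change. Until it is confirmed, instruct staff to apply the 12-month limit of the treatment section and the contraindication table. Check that screening forms and training material carry the same figure.

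The change is to wording only, with no added participants, procedures or analyses. Its drawback is that, if the stricter limit stands, a few breastfeeding women go without primaquine, and those with vivax go without radical cure while breastfeeding.
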